1.3 SCHEDULE OF ACTIVITIES

After the cultural adaptation of Somryst developed in study 1, we will then enroll 200 patients into the RCT to compare the effectiveness of the culturally adapted digital program of CBT-I (Spanish Somryst) to minimally enhanced usual care and to determine cost-effectiveness of the intervention. Summary data from our pilot study indicate that 94 people were screened over 6 months, 52% were found eligible, and 71% completed the study. In particular, our screening in one primary care clinic over two months resulted in 22 people screened, 77% were eligible, and 71% completed the first focus group. Our pilot data indicate that we are able to screen 8 patients/month and enroll patients/month from one clinic and that an accrual rate of 12/month from multiple clinics is reasonable. The specific list of measures and schedules of activities are represented in Table 1.

Table 1. List of Measures and Schedule of Activities

	Screening/ Enrollment	Baseline	Pre-Tx	Treatment	Post-Tx (9 weeks)	6-mo Follow -Up
Procedure/Assessment/Follow -Up Windows	Virtual or in person	Virtual or in person	14 days before tx	Through Week 9 of Study	Post-Tx (9 weeks)	6-mo Post- Tx
Sociodemographic information	Х					
Insomnia Severity Index	Х	Х		Х	Х	Х
Informed Consent/Enrollment	Х					
Permission for Future Contact and Use	х					
Sleep and Depression Medicines	х				Х	Х
Sleep Disorder	х					
CAGE Assessment	Х					
Assessment for Bipolar/Psychosis/ Schizophrenia	Х					
Health Care Coverage	Х					
Assessment for Cognitive Impairment	Х					
Language Proficiency	х					
Technology Use	Х					
Referral/Contact Information	Х					
Randomization				Х		
Generalized Anxiety Disorder (GAD-7)		Х		Х	Х	Х
Epworth Sleepiness Scale (ESS)	Х	Х			Х	Х

			1	-	1
Pittsburgh Sleep Quality Index (PSQI)	Х			X	X
Quality of Life (SF-12)	Х			Х	Х
Satisfaction with Care (PACIC)	Х			Х	Х
Health Literacy	Х				
Penn State Worry Questionnaire (PSWQ)	X				
Personal Health Questionnaire Depression Scale (PHQ-8)	Х		х		
Health Care Utilization	Х			Х	Х
Medical History	Х				
Dysfunctional Attitudes and Beliefs about Sleep (DBAS-16)	Х			X	Х
Hospitalization				Х	Х
Acceptability and satisfaction with intervention				X	
Actigraphy		Х		Х	
Usability and Net promoter questionnaire				Xa	
Sleep Diary		Х		Х	
Adverse Events			Х	Х	Х

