4.4 END-OF-STUDY DEFINITION

A participant is considered to have completed the study if he or she has completed the baseline assessment, at least 4 intervention sessions, and the 6-month follow-up assessments.

The end of the study is defined as completion of the 6-month follow-up assessment shown in the Schedule of Activities (SoA), **Section 1.3**.

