5 STUDY POPULATION

5.1 INCLUSION CRITERIA

In order to be eligible to participate in this study, an individual must meet all of the following criteria:

- 1. Provision of signed and dated informed screening consent form
- Stated willingness to comply with all study procedures and lifestyle considerations (see Section 5.3, Lifestyle Considerations) and availability for the duration of the study (8 months)
- 3. Males and females; Age 18-65
- 4. Adults with moderate insomnia symptoms as documented on initial eligibility screen based on validated cut-off for community samples (Insomnia Severity Index Score >10)
- 5. Willingness to adhere to the digital therapeutic treatment (study-app based intervention) or enhanced usual care study regimen
- 6. Be Spanish-speaking or bilingual (English and Spanish) adults
- 7. Self-identify as Hispanic or Latinx
- 8. Report experience of sleep disturbances for at least 3x/week
- 9. Report experience of sleep disturbances for at least 3 months

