6 STUDY INTERVENTION(S) OR EXPERIMENTAL MANIPULATION(S)

6.1 STUDY INTERVENTION(S) OR EXPERIMENTAL MANIPULATION(S) ADMINISTRATION

6.1.1 STUDY INTERVENTION OR EXPERIMENTAL MANIPULATION DESCRIPTION

Intervention Arm: digital CBT-I (Somryst), usual care, and sleep hygiene brochure.

Patients who are randomized to Somryst will receive the Spanish-language version of the culturally adapted Somryst, a self-guided digital program of CBT-I, the usual care provided by their PCP, and a sleep hygiene brochure. Somryst, is an interactive and tailored mobile-based program modeled on the primary tenets of face-to-face CBT-I, the web version has been shown to be effective at reducing insomnia symptoms.^{25,26}

Patients will be asked to complete six cores (main intervention content) during the 9-week intervention period (a new Core becomes available 7 days after completion of the previous one). After completing a Core, they can review that Core at any time, and access program worksheets from the My Stuff section of the mobile program (App).

The six cores are based on the primary treatment components provided in face-to-face cognitive behavioral therapy for insomnia.^{6,14} The Behavioral Cores incorporate sleep restriction and stimulus control, providing patients with a variety of "rules" to follow in order to retrain their bodies to associate sleep with bed. Stimulus control aims to reduce the anxiety or conditioned arousal individuals may feel when attempting to go to bed. Sleep restriction is a form of systematic mild sleep deprivation in which a sleep window is maintained to allow the body to relearn proper sleeping dynamics and increase sleep efficiency. The Educational Core (also called Sleep Hygiene) focuses on general education about sleep (e.g., understanding the different types of sleep problems) and improving sleep hygiene and other maladaptive behaviors (e.g., establishing regular sleeping schedules, eliminating napping, and avoiding nicotine, caffeine, exercise, and drinking alcohol before bedtime). The Cognitive Core (also called Cognitive Restructuring) attempts to address and change the negative beliefs and thoughts about sleep

18 May 2022

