that may exacerbate sleep difficulties. In addition to these main Cores, there are two other Cores: the Overview and Consolidation/Relapse Prevention Cores. These are critical for each user to receive in order to introduce intervention content and provide a rationale for the intervention (Overview); and integrate the educational, behavioral, and cognitive elements, promote adherence, generalize the information, help the user identify risk situations, and incorporate strategies to reduce relapse (Relapse Prevention).

Somryst relies on user-entered online Sleep Diaries to track progress and to tailor treatment recommendations (i.e., assign a "sleep restriction" window). Intervention content is enhanced through a variety of interactive features, including personalized goal-setting, graphical feedback based on inputted symptoms, animations/illustrations to enhance comprehension, quizzes to test user knowledge, patient vignettes, and video-based expert explanation.

The primary outcome, insomnia symptoms, will be assessed using the ISI at baseline, at post-intervention (9 weeks), and at a 6-month follow-up. Health-related quality of life, sleep quality, secondary outcomes, will also be assessed at the same endpoints as ISI. Daytime sleepiness, another secondary outcome will also be assessed at baseline and at the post-intervention (9 weeks), and 6-month follow-up visit. Satisfaction with care and sleep quality will be assessed at baseline and at post-intervention (9 weeks) and 6-months, and sleep duration and efficiency will be assessed 14 days prior to randomization and at post-intervention (9 -weeks).

Comparator Arm: minimally Enhanced Usual Care (mEUC)- (usual care + sleep hygiene brochure) Patients randomized to the mEUC condition will continue to receive the typical standard of care in that clinic from their primary care provider (which may include pharmacotherapy). We have labeled the condition "minimally enhanced" because patients will be provided with a sleep hygiene brochure. Minimally EUC was chosen as the comparator because it is of high clinical relevance, will allow us to determine if the adapted digital CBT-I is superior to usual care, and addresses ethical issues (i.e., identifying but not treating insomnia).⁷⁸ Patients randomized to mEUC will complete assessments on the same schedule as those randomized to the intervention arm.

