Study candidates who meet initial eligibility criteria and consent to participate will be invited to a virtual online visit where they will complete a baseline sociodemographic and psychosocial survey battery.

Secondary Outcomes:

Health-related quality of life will be assessed through the validated Short-Form 12 (SF-12), which is a 12item self-report inventory that generically measures quality of life; it yields a measure of global healthrelated wellbeing as 8 domain-specific subscores.⁸² This will be assessed at baseline and at postintervention (9 weeks) and 6-month follow-up.

Sleepiness will be measured with the 8-item Epworth Sleepiness Scale, a brief, validated self-report scale of daytime sleepiness with excellent psychometric properties.⁸³ This will be assessed at baseline and at post-intervention (9 weeks) and 6-month follow-up.

Satisfaction with care will be measured using a question adapted for this trial asking patients to rate the quality of professional care they have received for their symptoms of insomnia.⁸⁴ This will be assessed at baseline and at the post-intervention visit (9 weeks). Based on current best practices⁶⁶ of cultural adaptation of evidence-based interventions, we will also ask participants in the intervention group to

18 May 2022

rate their satisfaction with, as well as their difficulties with program content or activities after each online session.

Self-reported and actigraphy assessed wake after sleep onset and self-reported sleep onset latency will be assessed at baseline and at post-intervention for 14 days.

Sleep duration and sleep efficiency will be measured continuously and unobtrusively for 14 days following the baseline visit and post-intervention using the ActiWatch SpectrumPRO, a waterproof, lightweight, actigraphy-based device that measures physical activity continuously and can be worn for 24 hours daily. The validity of actigraphy for determining sleep duration in particular, compared with the gold standard polysomnography, is excellent.⁸⁵

Sleep quality will be measured at baseline, post-intervention, and at 6-months follow-up with The Pittsburgh Sleep Quality Index (PSQI),⁸⁶ which has excellent psychometric properties, and established validity among Spanish-speakers.⁸⁷

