Other Measures: *Sociodemographic Information* will be collected at screening including, age, sex, race, country of origin, educational attainment, nativity status, household income, employment status, and health insurance status. **Direct health care costs** will consist of the retail costs of Somryst (payer's costs plus patient out-of-pocket costs). Structured interviews will gather information about health care utilization (primary care, other ambulatory care, emergency department, or hospital visits). **Indirect costs** will include patients' lost productivity due to 1) participating in Somryst sessions, and 2) lost productivity related to poor sleep quality.

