Cost-effectiveness will be assessed based on the study observation period (9 weeks) in the main analysis, but micro- simulation analyses will simulate sustaining the insomnia prevention effects of CBT-I and EUC for years into the future, up to 10 years. Incremental cost-effectiveness ratios (ICERs) will be calculated as incremental change in costs divided by incremental change in QALYs comparing Somryst to mEUC).). ICERs will be assessed as follows (in 2021 U.S.): <50,000 per QALY gained will be considered cost-effective, \geq 50,000 and <150,000 of intermediate value, and \geq 150,000 of low value. Non-parametric bootstrapping with 1,000 random samples of all QALY and cost distributions

will be used to generate 95% uncertainty intervals for cost- effectiveness ratios.¹⁰⁰ Sensitivity analyses will test the robustness of the cost-effectiveness estimate to a range of inputs regarding intervention costs, productivity and quality of life losses related to chronic insomnia, size of quality of life improvement effect, and durability of intervention effect (ranging from one month to ten years). Cost-effectiveness analyses will be carried out and reported according to the Consolidated Health

Economic Evaluation Reporting Standards (CHEERS).¹⁰¹ Cost-effectiveness analyses will be carried out in TreeAgesoftware (TreeAge Inc., Williamstown, MA)

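### The main cost-effectiveness analysis stops at 9 weeks although participants are followed for about 35 weeks; the 6-month SF-12 has no stated economic use, and the cost window is undefined

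*Combined protocol and SAP*

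**What the plan says.** **Horizon.** Section 9.4.3 sets it: "Cost-effectiveness will be assessed based on the study observation period (9 weeks) in the main analysis". Elsewhere 9 weeks is the length of treatment; section 6.1.1 says "Patients will be asked to complete six cores (main intervention content) during the 9-week intervention period". Follow-up goes on after that. Section 4.4 says "The end of the study is defined as completion of the 6-month follow-up assessment", section 4.1 places that visit 6 months after treatment, and the synopsis and inclusion criterion 2 (section 5.1) give 8 months of participation.

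**Utilities.** Section 6.1.1 says that quality of life "will also be assessed at the same endpoints as ISI", and section 8.1 says of the SF-12: "This will be assessed at baseline and at postintervention (9 weeks) and 6-month follow-up". Section 9.1, however, derives utilities from the baseline and 9-week SF-12. Section 9.4.3 repeats this with baseline and post-intervention data.

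**Costs.** Table 1 (section 1.3) has a row for "Health Care Utilization". The column headings of that part of the table are lost in the text read here, but the row carries the same marks as the SF-12 and PSQI rows, whose timing section 8.1 confirms. Section 9.4.3 accumulates health care use in the main payer analysis over a follow-up period, and productivity losses over the time a participant is observed. Neither is given a length.

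**Beyond 9 weeks.** Section 9.4.3 adds a micro-simulation of up to 10 years and a sensitivity range for durability from one month to ten years. It classes an ICER below 50,000 per QALY as cost-effective, 50,000 to below 150,000 as intermediate, and 150,000 or more as low value.

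**Productivity.** Section 8.1 says indirect costs include "lost productivity related to poor sleep quality". Section 9.4.3 computes the loss as labor force participation rate times average earnings over the time observed. The sentence before says that interview answers on lost pay and absence from work will be analysed.

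**The concern.** The label does not fit the trial: what section 9.4.3 calls the observation period is only the treatment phase. Two consequences follow.

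First, the main analysis charges the whole program cost against the first quarter of follow-up. The utility measurement that could show whether the gain lasts is collected but has no stated economic use. The primary hypothesis in section 9.1 expects ISI scores to remain better at 6 months, so a lasting gain is not a remote case here.

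Second, it is not stated whether the 6-month health care data enter the main payer analysis. If they do, the ratio sets about 35 weeks of costs against 9 weeks of QALYs and is hard to interpret. If they do not, observed economic data go unused.

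The economic aim ends in a value class with fixed limits, so the choice of window can alter the stated conclusion.

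**Working it through.** **1. Length of follow-up.** The plan's own figure is 8 months. 9 weeks + 6 months × 4.348 weeks = 35.1 weeks; 35.1 / 4.348 = 8.07 months. This reproduces it. With 6 months rounded to 26 weeks, follow-up is 9 + 26 = 35 weeks, and 9 / 35 = 25.7%.

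**2. Possible mismatch.** If health care use runs to the 6-month visit and QALYs stop at week 9, the cost window is 35 / 9 = 3.9 times the QALY window. The direction of the resulting error depends on the difference in use between arms, which the documents do not give.

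**3. Effect of the horizon on the ICER.** The documents give no program cost and no expected utility gain. Assume a positive between-arm gain and equal health care use, so that the incremental cost is the same for both horizons. The ICER ratio is then the ratio of utility-weeks.

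Utility-weeks up to week 9, per unit of gain:
- immediate gain: 9
- gain building to week 5, when the sixth Core can first open (5 × 7 = 35 days): 0.5 × 5 + 4 = 6.5
- gain building to week 9: 0.5 × 9 = 4.5

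Utility-weeks added from week 9 to week 35: 0 if the gain stops; 0.5 × 26 = 13 if it fades linearly to zero; 26 if it is held.

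9-week ICER divided by 35-week ICER:

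| After week 9 | Immediate | Builds to week 5 | Builds to week 9 |
|---|---|---|---|
| Stops | 9/9 = 1.0 | 6.5/6.5 = 1.0 | 4.5/4.5 = 1.0 |
| Fades to zero | 22/9 = 2.4 | 19.5/6.5 = 3.0 | 17.5/4.5 = 3.9 |
| Held | 35/9 = 3.9 | 32.5/6.5 = 5.0 | 30.5/4.5 = 6.8 |

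**4. Value class.**
- Factor 1.0: no ICER changes class.
- Factor 2.444: 50,000 × 2.444 = 122,222 and 150,000 × 2.444 = 366,667. A 9-week ICER from 50,000 to about 122,000 becomes cost-effective, and one from 150,000 to about 366,000 leaves low value. One between about 123,000 and 149,000 stays intermediate, and one above about 367,000 stays low.
- Factor 6.778: 150,000 × 6.778 = 1,016,667. Every 9-week ICER from 50,000 to about 1.0 million changes class.

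**5. What three SF-12 assessments would give.** Joining baseline, week 9 and week 35 by straight lines, with r the 6-month gain as a share of the 9-week gain, the factor is (4.5 + 13(1 + r)) / 4.5. This is 3.9 at r = 0, 5.3 at r = 0.5 and 6.8 at r = 1. At r = 0 the line assumes a gradual fade. If the gain in fact stopped just after week 9, the true factor would be 1.0 and the calculation would still return 3.9.

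**6. Productivity formula.** Participation rate × earnings × time observed is the amount a person of that age would be expected to earn. Two participants of the same age observed for the same time receive the same value however much work they missed. The formula contains no lost time, and its link to the interview answers is not written.

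**The case against.** The strongest case is that 9 weeks was chosen on purpose. Section 3 defines the SF-12 endpoint from baseline to 9 weeks and justifies it by the economic analyses, and section 9.1 uses the same two assessments for utilities. Later time is covered by the simulation, and the durability range of one month to ten years includes persistence to 6 months. All of this stands: a 9-week base case is not in itself an error. What remains is that the label is wrong and that durability is to be modelled without any statement that the trial's own 6-month utilities inform it.

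A reader might infer that the 6-month health care data have no economic role. The documents do not support that. Section 9.4.3 puts cumulative use into the main payer analysis, and follow-up in this protocol often means the 6-month visit. The gap is that inclusion is not stated. Nor is the 6-month SF-12 idle, since section 9.4.2 repeats the analyses of secondary endpoints at 6 months; it lacks only an economic use.

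A reader might also infer that the plan cannot measure productivity loss. That is too strong, because interview data on missed work are to be analysed and productivity losses are varied in sensitivity analyses. The formula and those data are simply not connected, and the point touches only the secondary patient-perspective analysis.

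Finally, a longer window has its own weakness: linear interpolation over 26 weeks without an SF-12 assessment can overstate QALYs, as step 5 shows. This stands and should be declared.

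**Conclusion.** The concern holds as an inconsistency in section 9.4.3 that is worth correcting. Nine weeks is about 26% of the follow-up, the 6-month SF-12 is named in no economic analysis, and the windows for health care use and productivity have no stated length.

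The size is conditional. With a positive gain and equal health care use between arms, the 9-week ICER is 1.0 to 6.8 times the 35-week ICER under the assumed curves. A change of value class is possible and not certain. The documents do not support saying that the program will be misclassified, or by how much, because they give neither a cost nor a utility gain. The productivity formula, read alone, yields expected earnings and not a loss. None of this touches the ISI analysis.

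**What to change.** - Use one window for costs and QALYs in the within-trial analysis, from baseline to 6 months post-intervention, with QALYs as the area under the curve of the three SF-12 assessments. Report the 9-week result beside it as a sensitivity analysis. The 9-week SF-12 clinical endpoint need not change.
- Correct the observation-period label, and state the start and end of the window for each cost item.
- Use the observed 6-month utility difference to inform the durability assumption in the simulation, and say how.
- Compute productivity loss as reported lost work time multiplied by the earnings figures. First confirm that the interviews capture lost time, since the legible part of Table 1 lists no such item.

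The cost is SAP wording and analysis code. SF-12 and health care use are already scheduled at 6 months, so they need no new collection. There are two downsides to state. Missing data may be greater at 6 months than at 9 weeks, by an amount the documents do not give; the missing-data text in section 9.4.2 is written for the mixed models, so a method for missing utilities and costs must be added. Interpolation from week 9 to 6 months overstates QALYs if the gain ends soon after week 9 (factor 3.9 against a true 1.0 in the extreme case), which is the reason to keep the 9-week result in the report.

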6.3 MEASURES TO MINIMIZE BIAS: RANDOMIZATION AND BLINDING

Randomization. After completing the baseline assessment, patients will be randomly assigned in a 1:1 ratio to either the Culturally Adapted Somryst or minimally Enhanced Usual Care (mEUC) condition. Randomization will be generated by a computerized random-number sequence programmed by the study statistician and implemented in the secure, password-protected, encrypted data tracking program. The sequence will be unknown to research assistants enrolling patients.

Blinding. One research staff member (TBN) will be responsible for randomizing participants and so this research assistant and the PI will be unblinded to study condition. Participants will also be unblinded to study condition since treatment conditions will be obvious to them. Research assistants conducting the post-intervention (9 weeks) and 6-month outcome assessments will be blinded to participants' treatment condition, as this is preferred to minimize risk of bias in outcome ascertainment.

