9.2 SAMPLE SIZE DETERMINATION

Prior studies suggest that CBT-I yields approximately an 8-point reduction in the ISI, our primary measure of insomnia, with the standard deviation (SD) of post-intervention change scores being 4 to 5 points. Our expectation is that the improvement in patients assigned to the intervention condition (Somryst) will be 8 points or greater, and that those assigned to minimally enhanced usual care (mEUC) will exhibit a 5-point improvement. Typically, we expect the SD of change scores to increase for longer intervals (e.g., 6 or 12 months), and have therefore conservatively based our power calculations on a SD (change) of 6.0. Accordingly, randomization of 200 patients to Somryst versus mEUC (1-to-1 ratio) will provide 90% power to detect a differential reduction (post-intervention and 6-month follow-up) in ISI of 3 points or larger, using a 2-tailed Wald chi-square test of the appropriate contrast. This sample size estimate allows for up to 15% attrition, such that we have baseline data on all 200 patients (collected prior to randomization), but follow-up data on only 170.

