9.4.2 ANALYSIS OF THE PRIMARY ENDPOINT(S)

Mixed-model RM-ANOVA will be used to estimate and compare the changes in the primary endpoint (ISI) and other patient-important outcomes (e.g., insomnia symptom severity, daytime sleepiness) between Somryst and mEUC. The RM-ANOVA model will include Group (Somryst versus mEUC), Time (baseline, post-intervention and 6-month follow-up), and the Group × Time interaction as fixed factors with an unstructured residuals covariance matrix. This will yield estimates of the within-group means and standard errors at each assessment. Specific interaction contrasts (e.g., Group × Pre-vs-Post Intervention) will be estimated to estimate the magnitude and test the statistical significance of the differential change in insomnia symptoms using the Wald χ^2 statistic. We will plot the mean insomnia scores across assessments, stratified by treatment group, to elucidate the nature of the interaction (i.e., whether Somryst resulted in significantly greater improvements [or lesser worsening] than mEUC). If, despite randomization, the two groups differ substantially (p<0.10 after stepdown Bonferroni correction) on one or more sociodemographic or clinical factors assessed at baseline, sensitivity analyses will be performed in which these factors are included as covariates in the RM-ANOVA, in order to rule out the possibility that the results from the primary analyses are attributable to group differences on these factors. The same analyses will be repeated to estimate and compare changes in the primary endpoint and secondary endpoints between Somryst and mEUC at 6-months.

Significance will be evaluated with a two-tailed p value of 0.05. To control for multiplicity, postintervention will be evaluated first and if significant timepoints post-intervention and 6-months followup will be evaluated. In addition, estimated marginal means \pm 95% confidence intervals will be calculated for each assessment point and Cohen's d will be used as an estimate of effect size for the change from baseline to each assessment point.

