9.4.3 ANALYSIS OF THE SECONDARY ENDPOINT(S)

For secondary endpoints, , we will follow Hochberg's step-up approach as outlined in Figure 2.

Figure 2. Decision structure for hypothesis testing of primary and secondary endpoints

Coupled with our primary hypothesis that CBT-I will result in improved ISI scores, a secondary hypothesis is that CBT-I will result in *greater improvement in* quality of life, as captured by the more general SF-12 that will be measured pre- and post-intervention in both the CBT-I and mEUC participants. We will use the validated method of Brazier et al. to calculate utilities (QALY penalties) from baseline and post-intervention SF-12 data by first mapping responses to the simpler SF-6D scale and then using a regression model to estimate single index scores.^{97, 98}_The cost-effectiveness analysis will compare incremental costs and quality-adjusted life years (QALYs) gained in the CBT-I arm compared with mEUC. The primary cost-effectiveness analysis will be from the payer's point of view (government, insurer, or health

18 May 2022

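### The cost-effectiveness analysis does not define the QALY or specify adjustment for baseline SF-6D utility, which gives up precision in the ICER denominator

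*Combined protocol and SAP*

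**What the plan says.** Section 9.4.3 of the combined protocol and SAP uses a published mapping "to calculate utilities (QALY penalties) from baseline and post-intervention SF-12 data". The regression mentioned there converts SF-12 responses to a single index score; it is a scoring step, not covariate adjustment. The ratio is then defined: "Incremental cost-effectiveness ratios (ICERs) will be calculated as incremental change in costs divided by incremental change in QALYs comparing Somryst to mEUC". The main analysis covers the 9-week observation period, uncertainty comes from 1,000 non-parametric bootstrap samples, and the result is placed in value bands cut at 50,000 and 150,000 per QALY. The listed sensitivity analyses vary inputs such as intervention cost, size of the quality-of-life effect and durability.

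Section 8.1 confirms that the SF-12 is taken at baseline, and Section 9.4.2 expects no missing baseline data. Table 1 in Section 1.3 also has a row for "Health Care Utilization" that reads as marked at baseline, 9 weeks and 6 months, with no recall period.

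The only covariate rule is in Section 9.4.2. It is a sensitivity analysis of the RM-ANOVA, triggered by a baseline difference at p<0.10 after step-down Bonferroni correction. It is not extended to the cost-effectiveness analysis.

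**The concern.** With two utility measurements nine weeks apart, baseline utility supplies half of an area-under-the-curve QALY and also predicts the other half. An unadjusted comparison of such QALYs carries any chance baseline difference into the incremental QALY. If QALYs are instead changes from baseline, the same difference enters with the opposite sign, because utilities regress to the mean. Regression on baseline utility removes the dependence in both cases.

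The incremental QALY is the denominator of the ICER. Over nine weeks it is a small number, and a denominator with an appreciable chance of falling at or below zero makes the ratio, its bootstrap interval and the value band unstable. The plan leaves open both the construction and the adjustment, and the construction decides how much precision is at stake.

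**Working it through.** **The plan's own figure.** The only power statement concerns the ISI: the sample "will provide 90% power to detect a differential reduction" "in ISI of 3 points or larger", and the authors "conservatively based our power calculations on a SD (change) of 6.0". The test level is given by: "Significance will be evaluated with a two-tailed p value of 0.05". Patients are "randomly assigned in a 1:1 ratio", so there are 100 per arm, and 85 per arm after 15% attrition.
- SE = 6.0 × √(2/85) = 0.920
- 3/0.920 = 3.26, and 3.26 − 1.96 = 1.30, which gives power of 0.90. The figure reproduces.

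Nothing comparable is stated for QALYs or costs.

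**Inputs for the QALY check.**
- From the documents: T = 9/52 = 0.173 year; n = 85 per arm with follow-up.
- Assumed, because the documents are silent: SF-6D SD 0.12 (range 0.10-0.15), equal at both times; baseline to 9-week correlation r = 0.6 (range 0.4-0.75); true 9-week utility gain 0.03, with 0.05 and 0.08 as alternatives.

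**Expected QALY gain** = gain × T/2: 0.03 × 0.0865 = 0.0026; 0.05 × 0.0865 = 0.0043; 0.08 × 0.0865 = 0.0069.

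**SE of the QALY difference** = (T/2) × SD × √(2/n) × √f. The common part is 0.0865 × 0.12 × √(2/85) = 0.00159. The chance of an estimate at or below zero is Φ(−gain/SE), by normal approximation.

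| QALY construction | f | SE | Gain 0.03 | Gain 0.05 | Gain 0.08 |
|---|---|---|---|---|---|
| Raw area under the curve | 2+2r = 3.2 | 0.00285 | 18.1% | 6.4% | 0.8% |
| Change from baseline | 2−2r = 0.8 | 0.00142 | 3.4% | 0.1% | <0.1% |
| Regression on baseline | 1−r² = 0.64 | 0.00127 | 2.1% | <0.1% | <0.1% |

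Simulation at a gain of 0.03 gave 18.7% raw and 2.3% adjusted. A simulation of 20,000 trials at a gain of 0.04 gave SEs of 0.00286, 0.00143 and 0.00128, and chances of 11.7%, 0.7% and 0.4%.

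**Variance saved by adjustment.**
- Against raw QALYs: 1 − (1−r²)/(2+2r) = (1+r)/2, which is 70% at r = 0.4 and 87.5% at r = 0.75.
- Against change-based QALYs: 1 − (1−r²)/(2−2r) = (1−r)/2, which is 30% at r = 0.4 and 12.5% at r = 0.75.

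**Error given an observed imbalance.** One SE of the baseline difference is 0.12 × √(2/85) = 0.0184.
- Raw QALYs shift by (1+r) × 0.0184 × T/2 = 0.00255, or 98% of the gain at 0.03. Over SD 0.10-0.15, r 0.5-0.7 and 85-100 per arm, the share is 71-130% at a gain of 0.03, 42-78% at 0.05 and 27-49% at 0.08.
- Change-based QALYs shift the other way by (1−r) × 0.0184 × T/2 = 0.00064, or 25% of the gain at 0.03. Over the same ranges the share is 14-38% at 0.03 and 8-23% at 0.05.
- After regression on baseline utility the shift is zero.

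**Costs.** The documents give no cost means, SDs or correlations, so no figure can be computed.

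**The case against.** The strongest objection is that the plan never says QALYs are raw areas under the curve. Its talk of QALYs gained and of incremental change, and its framing of the SF-12 endpoint as change from baseline in Section 3, fit a change-based QALY at least as well. On that reading adjustment lowers the SE only from 0.00142 to 0.00127, about 10%. This stands, and it is why the construction must be stated. Even so, adjustment is never less precise under either construction in these calculations.

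A reader might infer that chance imbalance can match the whole 9-week QALY gain. The documents do not support that as a general statement. It requires raw area-under-the-curve QALYs and a utility gain of about 0.05 or less. For change-based QALYs, the probability of an imbalance that large is below 1% at gains of 0.03 or more.

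A reader might also infer that the ICER would be biased, or its sign decided by luck. Under 1:1 randomization the unadjusted difference is unbiased, and the bootstrap interval carries chance imbalance. The planned sensitivity analyses further mean that the conclusion does not rest on one point estimate, although none of them replaces adjustment.

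Finally, baseline utilization appears only as a row in Table 1 without a recall period, so adjusting costs first needs a baseline window and costing rules.

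**Conclusion.** The point holds as an omission that costs precision. The QALY formula is not stated, no baseline adjustment is specified for the cost-effectiveness analysis, and the covariate rule in Section 9.4.2 does not reach it. The plan is silent on adjustment; it does not rule it out.

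The size depends on what the plan leaves open. If QALYs are raw areas under the curve, the loss is large: adjustment more than halves the SE in the central case. If they are changes from baseline, the gain from adjustment is modest. Every figure rests on the assumed SD, correlation and utility gain, and the chance of a non-positive estimate is especially sensitive to the gain. No size can be given for costs. This refines a secondary economic analysis and does not touch the primary ISI comparison.

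**What to change.** In Section 9.4.3:

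1. State how each patient's QALY is computed from the baseline and 9-week utilities.
2. Estimate incremental QALYs by regressing each patient's QALYs on arm and baseline SF-6D utility.
3. Refit that model in every bootstrap replicate, resampling patients so that each patient's cost and QALY stay paired.
4. Use the adjusted difference for the ICER and its uncertainty interval.
5. If a recall period for baseline utilization can be defined, adjust costs for baseline utilization in the same way.

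The QALY part needs a few sentences of SAP text, one regression and no new data. The cost part also needs a defined baseline window and a way of costing it. Both are best settled before outcome data by arm are seen.
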